1.0 PROTOCOL OVERVIEW (SCHEMA)

Eligible metastatic prostate cancer patients >/= M1a (castration naïve)

PSA Testing, Bone scan, CT abdomen, Pelvic MRI

Baseline 18F FluciclovinePETCT before initiation of SST

22-28 weeks of SST

PSA Testing, Bone scan, CT abdomen, Pelvic MRI

Repeat 18F FluciclovinePETCT

2.0 Background and Rationale

In screened populations, the incidence of metastatic prostate cancer (M1 PC) at diagnosis is approximately 1.5%.¹ In the general population, the incidence of M1 PC at diagnosis is approximately 5%.² Thus, men presenting with M1 PC at diagnosis represent close to one third of the 30,000 men dying from PC each year in the US. The treatment paradigm for M1 and clinically node positive (cN1) PC is centered on use of systemic therapies, commencing with androgen deprivation therapy (ADT) followed by secondary hormonal treatments and then chemotherapy upon the development of castrate resistance, while definitive local therapy has traditionally been reserved for treatment of localized PC.³ However, a growing body of evidence suggests that definitive treatment of the primary tumor may improve the outcome of men with advanced disease. First, two recent prospective randomized trials have shown a survival benefit for men with locally advanced disease that received radiation therapy in addition to ADT compared to those receiving ADT alone.^{4,5} Second, retrospective studies suggest overall survival (OS) and cancer specific survival (CSS) are better in patients with pathologically proven lymph node positive disease that went on to receive treatment (radiation or prostatectomy) of their primary tumor.⁶⁻⁸ Third, it has been estimated that 24-44% of men treated with non-curative intent will develop symptomatic local progression requiring intervention.^{9,10} Symptomatic progression of local disease is a source of intense suffering as well as health care resource spending, consumed in hospital admissions and unsatisfactory palliative procedures, and is likely to accelerate death from PC.⁹ While salvage cystoprostatectomies and pelvic exenterations can offer palliation of symptoms, they carry a high rate of complications and can only be offered to a subset of men in this situation.^{11,12}

From a biological perspective, recent data suggest that ADT may not provide sufficient control of the primary tumor, which may act as a continued source for additional metastatic spread and resistant clonal selection.¹³⁻¹⁵ While there is evidence that demonstrates prostate cancer has significant heterogeneity within the multiple foci of tumors with a gland, molecular and cytogenetic data show that multiple metastases within the same patient are clonally related¹⁶⁻¹⁸ suggesting that metastatic clones may arise from a selective advantage of individual clones and that further systemic therapies may select for cells with varying malignant potentials. Therefore, definitive treatment of the primary tumor may also improve outcomes by removing a major source of spread and thereby increasing freedom from local and distant progression, delaying time to castrate resistance and prolonging time to fatal metastatic burden, thus resulting in prolongation of overall survival.

In this context, it will be important to develop a potential imaging biomarker for assessing response to SST which can potentially differentiate responders vs non-responders early in the course of treatment. It is possible that SST might significantly benefit only a subset of patients and imaging biomarker could allow risk stratification and possible incorporation of alternative therapies at a time when they would be expected to be most effective.

Multiple positron emission tomography (PET) tracers are available to evaluate patients with prostatic cancer, including fluorine-18 fluorodeoxyglucose (18F-FDG), 11C-choline, PSMA and 18F FLT. However, these tracers have a limited role in the evaluation of response to therapy. Hence, there is a need for a radiotracer that can be used to more accurately assess response to therapy. 18F-fluciclovine, is a Federal Drug Administration (FDA) approved imaging agent that is used to identify disease recurrence after definitive treatment in response to a rising PSA. It is a radiolabeled leucine analog (1-amino-3- fluorocyclobutane-1-carboxylic acid in the 'anti' configuration [18F-fluciclovine]) and used to depict amino acid transportation. Amino acid transporters and amino acid metabolism are up-regulated in multiple malignancies, including prostate cancer. 18F-fluciclovine has been shown to accumulate within prostate cancer.^{19,20}Although 18Ffluciclovine18F-fluciclovine has been approved for the evaluation of occult disease at the time of biochemical recurrence, this tracer also exhibited excellent in vitro uptake in the DU145 prostate carcinoma cell line and within orthotopically implanted prostate tumors in nude mice.¹⁹ Moreover, since only a small fraction of 18Ffluciclovine is excreted through the urinary tract early after injection, its imaging characteristics are favorable in the prostate. 18F-fluciclovine has been found to be successful in the assessment of primary and metastatic prostate cancer.²¹⁻²³ In a study of 21 patients, 18F-fluciclovine uptake in patients with prostate cancer was nearly 2-fold greater than that in patients with normal tissue.²⁴ Schuster et al²² found a moderate correlation between 18F-fluciclovine uptake and cancer aggressiveness. Although 18F-fluciclovine has been shown to successfully image prostate cancer, there is currently no evidence that changes in 18F-fluciclovine avidity correlate with changes in tumor burden or patient outcomes. Before 18F-fluciclovine is used for evaluation of the tumor response, the association of 18F- fluciclovine avidity and the tumor response must be established. The purpose of this pilot study is to assess the ability of 18F-fluciclovine positron emission tomography computed tomography (PET CT) to determine the therapeutic response to SST in patients with metastatic prostate cancer (M1PC).

3.0 Study Objective

Primary objective: Evaluate metabolic response by 18F-fluciclovine PET qualitatively and semi-quantitatively with standardized uptake values (SUV) following standard systemic therapy at 22-28 weeks (+/- 4 weeks) and correlate the findings with size changes as defined by conventional imaging and PSA response.

Secondary objectives:

- 1. To correlate pelvic 18F-fluciclovine PET imaging findings with pathologic findings at radical prostatectomy and pelvic lymph node dissection to determine 18F-fluciclovine PET imaging sensitivity and specificity for pelvic lymph node cancer involvement.
- 2. To evaluate 18F-fluciclovine PET imaging response and its correlation with progression free survival (defined by PCWG2 criteria)
- 3. To determine if sites of progressive disease develop at the initial/prior site (diagnostic site) of metastases or in newly developed sites at the time of metastatic progression.
- 4. To evaluate metabolic response by 18F-fluciclovine PET semi-quantitatively with target to blood pool ratio (TBR) following SST at 22-28 weeks (+/- 4 weeks), and correlate the findings with size changes as defined by conventional imaging and PSA response.

4.0 Eligibility Criteria

For entry into this study, the following criteria must be met. Any exceptions from the

protocol specific selection criteria must be approved by the principal investigator, and MD Anderson Cancer Center IRB, prior to enrollment.

4.1 Inclusion Criteria

- 1. Male patients
- 2.18 years and older
- 3. Histologically or cytologically proven prostate carcinoma
- 4. Documented evidence of M1 disease by AJCC staging by Bone scan, computed tomography (CT) or magnetic resonance imaging (MRI) 5. Castration naive disease, no prior systemic therapy for prostate cancer

Planned to receive SST

- 5. ECOG PS 0 or 1
- 6. Ability to understand and willingness to sign informed consent

4.2 Exclusion Criteria

- 1. Known brain metastasis
- 2. Small cell carcinoma of the prostate

5.0 Research Design and Methods

5.1 Study Design

A prospective pilot study will consist of eligible patients referred from genitourinary multidisciplinary care center at the University of Texas at MD Anderson cancer Center. All eligible patients scheduled to receive SST for up to 28 weeks will be enrolled, and initial 18F-fluciclovine PET CT will be performed within four weeks before initiation of systemic therapy. The patient will receive SST for up to 28 weeks, and 18F-fluciclovine PET CT will be repeated within four weeks following SST. 18F-fluciclovine PET CT will be performed as per the standard institutional protocol (Appendix C.). Blinded image interpretation will be made by radiologists and nuclear medicine physician. All scans will be interpreted independently by two physicians. Areas of focal tracer uptake will be localized with the companion CT and classified as lesions of the prostate, pelvic nodes, extrapelvic nodes, visceral, and bone lesions. Three- dimensional regions of interest will be placed in areas of tracer uptake, and measures of 18F- fluciclovine avidity will be recorded; the measures include SUVmax (body weight), metabolic tumor volume (MTV; volume of tumor [cm3] with SUV >42% of SUVmax), SUVmean (within the MTV), and total lesion avidity (TLA; calculated as MTV x SUVmean). A background SUVmax will be documented for each examination. On both pretreatment and posttreatment scans, the lesion SUVmax will be corrected for the background as follows: corrected SUVmax = lesion SUVmax background SUVmax. When the correct SUVmax is less than 0, 0 will be recorded. Similar corrections will be made for SUVmean. When the corrected SUVmax and the corrected SUVmean are 0 on posttreatment scans, MTV and TLA will also be recorded as 0. The percentage of change in the 18Ffluciclovine SUVmax after therapy will be calculated as follows: [(pretreatment corrected SUVmax posttreatment corrected SUVmax)/pretreatment corrected SUVmax] x 100. Similar calculations will be performed for SUVmean, MTV, and TLA.

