5.2 Reference standard

We will calculate tumor response by using RECIST 1.1 for visceral, bone and lymph node metastasis.²⁵ Primary tumor within the prostate gland will be assessed based on percent reduction in tumor size, changes in restricted diffusion and ADC value on mp pelvic MRI.²⁶⁻²⁸ In patient with available pathological specimen following prostatectomy and pelvic LN dissection, the pathologic response will be used to assess tumor response as well as identification of involved lymph nodes to assess for specificity and sensitivity of F18 Fluciclovine to detect occult lymph node involvement. Patients will be dichotomized by PSA measurement is taken at six months, PSA \leq 4 and PSA > 4.²⁹

Response assessment **Evaluation of Target lesions** Complete Response (CR) Disappearance of all target lesions. Any pathological lymph nodes (whether target or non-target) must have reduction in short axis to <10 mm. Partial Response (PR) At least a 30% decrease in the sum of diameters of target lesions, taking as reference the baseline sum diameters. At least 17% increase in median ADC value within the tumor on DWI MR images. Progressive Disease (PD): At least a 20% increase in the sum of diameters of target lesions, taking as reference the smallest sum on study (this includes the baseline sum if that is the smallest on study). In addition to the relative increase of 20%, the sum must also demonstrate an absolute increase of at least 5 mm. (Note: the appearance of one or more new lesions is also considered progression). Stable Disease (SD): Neither sufficient shrinkage to qualify for PR nor sufficient increase to qualify for PD, taking as reference the smallest sum diameters while on study. Evaluation of non-target lesions Complete Response (CR): Disappearance of all non-target lesions and normalization of tumor marker level. All lymph nodes must be non-pathological in size (<10mm short axis). Non-CR/Non-PD Persistence of one or more non-target lesion (s) and/or maintenance of tumor marker level above the normal limits. Progressive Disease (PD): Unequivocal progression (see comments below) of existing non-target lesions. (Note: the appearance of one or more new lesions is also considered progression).

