6.0 Statistical Considerations

Objectives, Endpoints, and Study Design

The primary objective of this prospective study is to evaluate the ability of 18F Fluciclovine PET CT to determine the therapeutic response to SST. All eligible patients will be imaged by 18F Fluciclovine PET CT before and after treatment. Treatment responders were defined as the posttreatment PSA level <= 4.0 ng/mL, and >4.0 ng/mL for non-responders. The primary endpoint is the percentage change of 18F-fluciclovine SUVmax. Secondary endpoints include the size changes defined by conventional imaging; TBR; sensitivity, specificity, positive predictive value (PPV), and negative predictive value (NPV) when comparing 18 F Fluciclovine PET CT imaging findings with pathologic findings; progression free survival defined by PCWG2 criteria; and the types of metastatic progression sites. The accuracy of using the percentage change of 18F- Fluciclovine SUVmax to discriminate treatment responders from non-responders is evaluated using Receiver Operating Characteristic (ROC) curve analysis.

Sample Size and Power Calculation

We wish to enroll 41 evaluable patients. With an overall sample size of 41 and an estimated 70% response rate, we expect approximately 28 responders and 13 non-responders. With these numbers, we will have 83% power to detect a difference of 0.26 between the area under the ROC curve (AUC) under the null hypothesis of 0.50 and an AUC under the alternative hypothesis of 0.76 using a two-sided z-test at a significance level of 0.05. Considering a drop-out rate of 10%, the total sample size required is 45.

Analysis Plan

Patient characteristics and clinical outcomes will be summarized using frequencies, mean, standard deviation, median, and range. Accuracy of predicting responders using the percentage changes of SUVmax or the size changes by conventional imaging will be analyzed by ROC curves. AUC will be compared using the nonparametric method described by Delong (1988). Optimal cut- off points for dichotomizing the percentage changes of SUVmax or the size changes will be selected by maximizing the Youden's index. Dichotomized values will be compared using the McNemar's test. Sensitivity, specificity, PPV, and NPV to correlate dichotomized 18 F Fluciclovine PET CT imaging findings with pathologic findings will be estimated along with 95% confidence intervals.

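### Is the primary ROC analysis undefined because no rule turns several lesions, new lesions and two readings into one SUVmax change per patient?

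*Combined protocol and SAP*

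**What the plan says.** Section 6.0 states: "The primary endpoint is the percentage change of 18F-fluciclovine SUVmax". That change is the ROC marker for separating PSA responders (posttreatment PSA at or below 4.0 ng/mL) from non-responders. The sample size paragraph counts patients: with 41 evaluable, "we expect approximately 28 responders and 13 non-responders".

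The marker is built in Section 5.1. Areas of uptake are "classified as lesions of the prostate, pelvic nodes, extrapelvic nodes, visceral, and bone lesions". At this step "the lesion SUVmax will be corrected for the background as follows", using a background SUVmax recorded for each examination, and negative results are set to 0. Then "The percentage of change in the 18Ffluciclovine SUVmax after therapy will be calculated as follows": pretreatment minus posttreatment corrected SUVmax, divided by the pretreatment value, times 100. Reading is blinded, and "All scans will be interpreted independently by two physicians".

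For conventional imaging, Section 5.2 uses RECIST 1.1 for visceral, bone and nodal metastases. Partial response requires "At least a 30% decrease in the sum of diameters of target lesions", and "the appearance of one or more new lesions is also considered progression". The prostate primary is assessed separately on MRI. The Analysis Plan in Section 6.0 compares SUVmax change with size change by the DeLong method and, after Youden cut-offs, by McNemar's test.

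**The concern.** Eligible patients have M1 disease, so many will have more than one lesion, and the text sets out no route from lesions to patients. It names no index lesion and no hottest-lesion, sum or mean rule. A lesion that appears only after treatment has no baseline to enter in the formula. A corrected baseline of 0 would mean dividing by zero. Two independent readings are taken with no rule for combining them. Section 5.2, by contrast, seems to give conventional imaging both a sum and a new-lesion rule.

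Two things would be at stake. If lesion values went into the ROC as separate observations, correlated lesions from one patient would be treated as independent and the evidence overstated. If the summary were chosen once PSA outcomes were known, the primary AUC, the Youden cut-off and the comparison with size change could all be steered.

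**Working it through.** **1. Which unit does the plan use?** Section 5.2 dichotomizes patients by PSA. Section 6.0 plans 41 evaluable patients, and 28 + 13 = 41. A lesion-level ROC would contradict those counts, so it is not the plan as written. The word lesion belongs to the background-correction step. The percentage formula has one pretreatment and one posttreatment corrected SUVmax and can be read as one value per scan.

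**2. Does the stated power fit one value per patient?** Inputs from Section 6.0: n1 = 28, n0 = 13, AUC 0.50 against 0.76, two-sided 0.05. Hanley-McNeil variance:

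V(A) = [A(1−A) + (n1−1)(A/(2−A) − A²) + (n0−1)(2A²/(1+A) − A²)] / (n1·n0)

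- A = 0.50: (0.25 + 27 × 0.0833 + 12 × 0.0833)/364 = 3.5/364 = 0.00962, SE 0.0981.
- A = 0.76: (0.1824 + 27 × 0.0353 + 12 × 0.0788)/364 = 2.081/364 = 0.00572, SE 0.0756.
- Power = Φ((0.26 − 1.96 × 0.0981)/0.0756) = Φ(0.897) = 81.5%, against the stated 83%.

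The stated figure is therefore consistent with 41 patient-level values.

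**3. How far apart can reasonable summaries be?** These are made-up corrected SUVmax values put through the plan's formula. Two lesions, 10 to 2 and 4 to 4:

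| Summary | Calculation | Reduction |
|---|---|---|
| Hottest baseline lesion, followed | (10−2)/10 | 80% |
| Hottest lesion on each scan | (10−4)/10 | 60% |
| Sum of lesions | (14−6)/14 | 57% |
| Mean of per-lesion changes | (80+0)/2 | 40% |

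The sign can change if a new lesion is hotter than the baseline one. One lesion going 6 to 2 plus a new lesion at 8 gives (6−2)/6 = 67% reduction (baseline lesion only), (6−8)/6 = 33% increase (hottest on each scan) or (6−10)/6 = 67% increase (sum). That case was constructed; the documents give no rate of new lesions.

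**4. What does that do to the AUC?** The AUC depends only on how patients are ordered, so a different percentage matters only if it changes that order. One non-responder is in 1/13 = 0.077 of the responder/non-responder pairs and one responder in 1/28 = 0.036. Those are the largest shifts from re-ranking one patient, against a design difference of 0.26 and a null standard error of 0.098. Shifts from several patients can add or cancel, and nothing in the documents indicates a direction.

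**5. Is the test valid under any of these summaries?** If SUVmax change is unrelated to PSA response, any summary computed without looking at PSA is also unrelated to it. The 5% level then holds for each. It would be lost only by choosing among summaries on their results.

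**6. Zero baselines and readers.** Regions are placed only where there is uptake, so a baseline at or below background should be uncommon, though its frequency is not given. Such a patient has no percentage change and would ordinarily be listed as not evaluable; the plan allows 45 − 41 = 4 patients for losses. Two readings can be averaged, settled by consensus or reported by reader.

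**7. Is conventional imaging better specified?** Only in part. The sum of diameters covers target lesions and leaves out the separately assessed primary. The new-lesion note assigns a progression category, not a number for a size-change ROC. Section 6.0 dichotomizes size change by Youden's index, not by RECIST category, so that note does not enter the comparison as written.

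**The case for a change.** The strongest reply is that knowing the patient is the unit does not say which value represents the patient, and reasonable values can differ in size and occasionally in sign. Section 5.1 does not say what readers are blinded to, and blinded reading would not in any case stop an analyst choosing a summary later. The study has a powered two-sided test and, under Section 5.10, is meant to support a multicenter application, so a reproducible marker matters. Settling the rule would cost only wording.

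Much of this stands. The rule is absent from the supplied text, and recording the summary before PSA is linked to the scans is good practice. If the best of three summaries were picked after seeing results, the 5% error rate would rise to between 8.4% and 13.5% (simulation with 28 and 13 patients, assumed correlation between summaries 0.9 down to 0.5). That figure presumes selection on results, which the plan neither proposes nor invites.

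It does not show that the plan gives a wrong answer, or that one summary is better. The hottest lesion may be the primary and mask change in metastases. Following baseline lesions ignores new disease. A sum is dominated by patients with many lesions. Choosing among these is a measurement decision for the investigators, and no concrete superior method has been put forward.

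**Conclusion.** No change to the plan follows. The text lacks detail on how one SUVmax change per patient is formed, and analysts can fill that gap with any of several ordinary summaries. The unit of analysis is clear from the patient counts, the power statement is consistent with it (81.5% against 83%), and a summary applied without reference to PSA keeps the 5% level. The effect on the AUC has no known direction and is bounded at 0.077 per re-ranked non-responder and 0.036 per re-ranked responder. The only stated rule that breaks down is the formula at a zero baseline, which should be uncommon.

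This rests on three assumptions: the summary is not chosen on its results, zero baselines are few, and the ROC is run on patients as Section 6.0 counts them. Lesion counts, reader agreement and new-lesion rates are not in the documents. Appendix C, cited for how the PET CT is performed, was not available and might hold a measurement rule.

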5.2 Reference standard

We will calculate tumor response by using RECIST 1.1 for visceral, bone and lymph node metastasis.²⁵ Primary tumor within the prostate gland will be assessed based on percent reduction in tumor size, changes in restricted diffusion and ADC value on mp pelvic MRI.²⁶⁻²⁸ In patient with available pathological specimen following prostatectomy and pelvic LN dissection, the pathologic response will be used to assess tumor response as well as identification of involved lymph nodes to assess for specificity and sensitivity of F18 Fluciclovine to detect occult lymph node involvement. Patients will be dichotomized by PSA measurement is taken at six months, PSA \leq 4 and PSA > 4.²⁹

Response assessment **Evaluation of Target lesions** Complete Response (CR) Disappearance of all target lesions. Any pathological lymph nodes (whether target or non-target) must have reduction in short axis to <10 mm. Partial Response (PR) At least a 30% decrease in the sum of diameters of target lesions, taking as reference the baseline sum diameters. At least 17% increase in median ADC value within the tumor on DWI MR images. Progressive Disease (PD): At least a 20% increase in the sum of diameters of target lesions, taking as reference the smallest sum on study (this includes the baseline sum if that is the smallest on study). In addition to the relative increase of 20%, the sum must also demonstrate an absolute increase of at least 5 mm. (Note: the appearance of one or more new lesions is also considered progression). Stable Disease (SD): Neither sufficient shrinkage to qualify for PR nor sufficient increase to qualify for PD, taking as reference the smallest sum diameters while on study. Evaluation of non-target lesions Complete Response (CR): Disappearance of all non-target lesions and normalization of tumor marker level. All lymph nodes must be non-pathological in size (<10mm short axis). Non-CR/Non-PD Persistence of one or more non-target lesion (s) and/or maintenance of tumor marker level above the normal limits. Progressive Disease (PD): Unequivocal progression (see comments below) of existing non-target lesions. (Note: the appearance of one or more new lesions is also considered progression).

